9.4 Analysis of the primary and key secondary variable(s)

9.4.1 Variable(s)

The primary efficacy variable is the change from baseline in VO_{2peak} (adjusted to body weight) at month 3.

The key secondary variable is the change from baseline in VO_{2peak} (adjusted to body weight) at week 6.

9.4.2 Statistical model, hypothesis, and method of analysis

The trial aims to establish the (alternative) hypotheses of superiority of LCZ696 vs enalapril.

The primary analysis will be performed comparing treatments with respect to the primary efficacy variable in an analysis of covariance (ANCOVA) model with the factors treatment and center and baseline VO_{2peak} as a covariate. The raw- as well as the adjusted (LS) group means will be presented. Additionally, a 95% confidence interval and a p-value will be given for the treatment contrast.

The key secondary endpoint, the change from baseline in VO_{2peak} (adjusted to body weight) at week 6 will be analyzed using the same model. The significance level will not be adjusted for multiplicity, the result of the test for week 6 will be regarded as providing confirmatory evidence, only if the test of the primary hypothesis (month 3) is also significant (a-priori ordered hypotheses).

9.4.3 Handling of missing values/censoring/discontinuations

Missing values of VO_{2peak} will be replaced with the last observed value (LOCF). Since the trial aims to estimate which improvements are achievable under the respective treatment regimens, LOCF seems to provide meaningful estimates for this purpose.

9.4.4 Supportive analyses

In case of serious deviations from the normality assumptions, treatments may additionally be compared by a non-parametric test (Mann-Whitney-U-test). In case of a substantial rate of missing data (>15%) or strong imbalances between treatment groups, Multiple Imputation (MI) may be considered as a sensitivity analysis.

9.5 Analysis of secondary variables

9.5.1 Efficacy variables

Secondary efficacy variables are:

- Change in VE/VCO_2 slope after 6 weeks and 3 months

- Change in exercise capacity (Watt) at VAT after 6 weeks and 3 months
- Change in rate of perceived exertion during exercise (Borg Scale) after 6 weeks and 3 months

Secondary efficacy variables will be analyzed using ANCOVA models analogous to the analyses of the primary endpoint.

9.5.2 Safety variables

Safety assessments will be based mainly on the frequency of adverse events. Adverse events will be coded by primary system organ class and preferred term according to the Medical Dictionary for Regulatory Activities (MedDRA). An adverse event related to study drug is defined as one considered by the investigator to have a suspected relationship with the study drug. The adverse events will be summarized by the number and percentage of patients in each primary system organ class and preferred term. For summaries by severity of event, the most severe occurrence for a particular preferred term will be used for a given patient. Summary tables of adverse events by treatment and severity will be provided.

Multiple occurrences of the same AE or SAE in the same patient will be counted only once, using the worst severity and drug relationship.

In the data listings of adverse events, the severity of an AE, whether or not an AE is study drug related, and whether or not it is a serious AE, will be indicated.

Abnormal laboratory values or test results constitute adverse events only if they induce clinical signs or symptoms or require therapy.

Laboratory data will be summarized by presenting summary statistics of raw data and change from baseline values (means, medians, standard deviations, ranges) and by presenting number and percentage of patients with notable laboratory abnormalities according to Appendix 1.

Data from other tests (vital signs) will be listed, notable values will be flagged, and any other information collected will be listed as appropriate.

9.5.3 Resource utilization

Not required.

9.5.4 Health-related Quality of Life

See under 'secondary/ [REDACTED] endpoints' above.

9.5.5 Pharmacokinetics

Not applicable.

9.5.6 Pharmacogenetics/pharmacogenomics

Not applicable

9.5.7 Biomarkers

Not applicable

9.5.8 PK/PD

Not applicable

9.6 Interim analyses

Not applicable.

9.7 Sample size calculation

Existing data suggest that the difference between LCZ696 and enalapril in VO_{2peak} at month 3 may be about $1.5 \text{ mL kg}^{-1} \text{ min}^{-1}$ with a (common) SD of 3 (Guazzi et al. 1999; Lewis et al. 2007). Under these assumptions, 86 patients per treatment arm would be required to achieve 90% power on a 2-sided, 5% significance level. To compensate for some drop-out and other protocol deviations, 100 patients per treatment group (200 in total) will need to be enrolled into this trial. The above mentioned literature suggests that the treatment effect for the key secondary endpoint, VO_{2peak} after 6 weeks, might be of a similar magnitude, therefore, the sample size calculation above applies also for the key secondary endpoint.

10 Ethical considerations

10.1 Regulatory and ethical compliance

This clinical study was designed and shall be implemented and reported in accordance with the ICH Harmonized Tripartite Guidelines for Good Clinical Practice, with applicable local

regulations (including European Directive 2001/20/EC, US Code of Federal Regulations Title 21, and Japanese Ministry of Health, Labor, and Welfare), and with the ethical principles laid down in the Declaration of Helsinki.

10.2 Informed consent procedures

Eligible patients may only be included in the study after providing written (witnessed, where required by law or regulation), IRB/IEC-approved informed consent, or, if incapable of doing so, after such consent has been provided by a legally acceptable representative of the patient. In cases where the patient's representative gives consent, the patient should be informed about the study to the extent possible given his/her understanding. If the patient is capable of doing so, he/she should indicate assent by personally signing and dating the written informed consent document or a separate assent form. Informed consent must be obtained before conducting any study-specific procedures (i.e. all of the procedures described in the protocol). The process of obtaining informed consent should be documented in the patient source documents.

Novartis will provide to investigators in a separate document an informed consent form that complies with the ICH GCP guideline and regulatory requirements and is considered appropriate for this study.

Women of child bearing potential should be informed that taking the study treatment may involve unknown risks to the fetus if pregnancy were to occur during the study and agree that in order to participate in the study they must adhere to the contraception requirement for the duration of the study. If there is any question that the patient will not reliably comply, they should not be entered in the study.

10.3 Responsibilities of the investigator and IRB/IEC

The protocol and the informed consent form must be reviewed and approved by a properly constituted Institutional Review Board/Independent Ethics Committee/Research Ethics Board (IRB/IEC) before study start. A signed and dated statement that the protocol and informed consent have been approved by the IRB/IEC must be given to Novartis before study initiation. Prior to study start, the investigator is required to sign a protocol signature page confirming his/her agreement to conduct the study in accordance with these documents and all of the instructions and procedures found in this protocol and to give access to all relevant data and records to Novartis monitors, auditors, Novartis Clinical Quality Assurance representatives, designated agents of Novartis, IRBs/IECs, and regulatory authorities as required. If an inspection of the clinical site is requested by a regulatory authority, the investigator must inform Novartis immediately that this request has been made.

10.4 Publication of study protocol and results

Novartis assures that the key design elements of this protocol will be posted in a publicly accessible database such as clinicaltrials.gov. In addition, upon study completion and finalization of the study report the results of this trial will be either submitted for publication and/or posted in a publicly accessible database of clinical trial results.

11 Protocol adherence

Investigators ascertain they will apply due diligence to avoid protocol deviations. Under no circumstances should the investigator contact Novartis or its agents, if any, monitoring the trial to request approval of a protocol deviation, as requests to approve deviations will not be granted.

This protocol defines the study objectives, the study procedures and the data to be collected on study participants. Under no circumstances should an investigator collect additional data or conduct any additional procedures for any research related purpose involving any investigational drugs.

If the investigator feels a protocol deviation would improve the conduct of the study this must be considered a protocol amendment, and unless such an amendment is agreed upon by Novartis and approved by the IRB/IEC it cannot be implemented. All significant protocol deviations will be recorded and reported in the CSR.

- Packer, M. et al., 2002. Comparison of omapatrilat and enalapril in patients with chronic heart failure: the Omapatrilat Versus Enalapril Randomized Trial of Utility in Reducing Events (OVERTURE). *Circulation*, 106(8), pp.920–6. Available at: <http://www.ncbi.nlm.nih.gov/pubmed/12186794> [Accessed October 1, 2015].
- SOLVD Investigators, 1992. Effect of enalapril on mortality and the development of heart failure in asymptomatic patients with reduced left ventricular ejection fractions. The SOLVD Investigattors. *The New England journal of medicine*, 327(10), pp.685–91. Available at: <http://www.ncbi.nlm.nih.gov/pubmed/1463530> [Accessed September 13, 2015].
- SOLVD Investigators, 1991. Effect of enalapril on survival in patients with reduced left ventricular ejection fractions and congestive heart failure. The SOLVD Investigators. *The New England journal of medicine*, 325(5), pp.293–302. Available at: <http://www.ncbi.nlm.nih.gov/pubmed/2057034> [Accessed January 14, 2015].

13 Appendix 1: Clinically notable laboratory values

Clinically notable laboratory abnormalities for selected tests based on a percent change from baseline:

Hematology

RBC count >50% increase, >20% decrease

Hemoglobin >50% increase, >20% decrease

Hematocrit >50% increase, >20% decrease

WBC count >50% increase, >50% decrease

Platelet count >75% increase, >50% decrease

Blood Chemistry

ALT (SGPT) >150% increase

AST (SGOT) >150% increase

BUN >50% increase

Creatinine >50% increase

Total bilirubin >100% increase

CPK >300% increase

Alkaline phosphatase >100% increase

Potassium >20% increase, >20% decrease

Chloride >10% increase, >10% decrease

Calcium >10% increase, >10% decrease

Uric acid >50% increase

14 Appendix 2: Treatment guidelines for hyperkalemia (serum potassium greater than or equal to 5.3 mmol/L)

General principles

Elevation of potassium levels above the predefined values should be repeated and confirmed before any action is taken.

Any patient with a serum potassium ≥ 5.3 mmol/L after enrollment into the study requires regular, repeated checks of potassium concentration (beyond that prescribed in the protocol) until it is clear that the potassium concentration is stable and not rising into the range of concern (≥ 5.5 and < 6.0 mmol/L) or potential danger (≥ 6.0 mmol/L).

Patients with elevated potassium value will be managed according to the corrective actions outlined below. Hyperkalemia should be followed until resolution.

Corrective action for management of hyperkalemia

Serum potassium ≥ 5.3 and less than or equal to 5.5 mmol/L

- Confirm potassium concentration in a non-hemolyzed sample
- Reinforce low potassium diet and restriction of food/drinks with high potassium content (e.g. orange juice, melon, bananas, low-salt substitutes etc.)
- Review medical regimen (including dietary supplements and over-the-counter medications) for agents known to cause hyperkalemia. Consider reduction in dose or discontinuation of these agents:
 - Aldosterone antagonists (if they are believed to be the most likely cause of hyperkalemia)
 - Potassium-sparing diuretics (e.g. amiloride and triamterene) including in combination products with thiazide or loop diuretics
 - Potassium supplements, e.g., potassium chloride
 - Salt substitutes
 - Non-steroidal anti-inflammatory drugs (NSAIDs)
 - Cyclo-oxygenase-2 (COX-2) inhibitors
 - Trimethoprim and trimethoprim-containing combination products, such as trimethoprim/sulfamethoxazole fixed combinations
 - Herbal Supplements:
 - For example, Noni juice, alfalfa (*Medicago sativa*), dandelion (*Taraxacum officinale*), horsetail (*Equisetum arvense*), nettle (*Urtica dioica*), milkweed, lily of the valley, Siberian ginseng, hawthorn berries
- Repeat serum potassium measurement within 3 to 5 days
- If serum potassium remains ≥ 5.3 and ≤ 5.5 mmol/L, regularly monitor serum potassium levels to ensure stability (suggested once monthly)
- Consider down-titration of study medication, according to investigator's medical judgment.

Serum potassium > 5.5 and < 6.0 mmol/L

- Confirm potassium concentration in a non-hemolyzed sample
- Consider down-titration or temporarily discontinue study drug according to investigator medical judgment.
- Apply all measures outlined for serum potassium ≥ 5.3 and ≤ 5.5 mmol/L
- Repeat serum potassium measurement after 2-3 days
- If serum potassium < 5.5 mmol/L, consider resumption of study drug at lower dose with repeat potassium within 5 days

Serum potassium greater than or equal to 6.0 mmol/L

- Immediately discontinue study drug
- Confirm potassium concentration in a non-hemolyzed sample
- Urgently evaluate patient and treat hyperkalemia as clinically indicated
- Apply all measures outlined for serum potassium ≥ 5.3 and < 6.0 mmol/L

No resumption of study drug without individualized case discussion with and permission from Novartis medical monitor or his/her designee.

15 Appendix 3: Guidelines for the management of blood pressure

Guidelines

1. Investigator should monitor blood pressure closely
2. If symptomatic hypotension occurs:
 - a. Correct any treatable cause, e.g. hypovolemia
 - b. If hypotension persists, any antihypertensive drug and non-disease-modifying drugs, such as diuretics, CCBs, nitrates, and α -blockers, should be down-titrated or stopped first before down-titration of the study drug is considered
 - c. If hypotension persists, the study drug should be down-titrated or even temporarily withdrawn. The dose re-challenge and medications adjust guidelines described in [Section 5.5.5](#) should be adhered to as much as possible.

16 Appendix 4: Guidelines for the management of renal dysfunction

General principles:

Glomerular filtration rate in HF patients depends on intrinsic renal function and on a balance between afferent and efferent glomerular arterial tonicity. This tonicity is partly regulated by a stimulation of angiotensin II and could be affected by either study medication. Moreover, renal dysfunction may develop or may deteriorate in some patients after study drug administration. These recommendations have been developed to guide the investigators in managing patients with renal dysfunction after randomization.

Two types of response to serum creatinine increase are described:**Surveillance situation**

[figure not shown]
If, at any time after randomization, eGFR decreases by $\geq 25\%$ from baseline (Visit 2) (or if serum creatinine concentration increase to 2.5 mg/dL [221 $\mu\text{mol/L}$]), the investigator will check for potentially reversible causes of renal dysfunction such as:

[figure not shown]
- Non-steroidal anti-inflammatory drug intake, antibiotics, or other treatments known to affect creatininemia
- Volume decrease, including that resulting from excessive dosing of diuretics
- Urinary infection
- Urinary tract obstruction
- Study medication

[figure not shown]
Action situation

[figure not shown]
If a patient eGFR decreases by $\geq 40\%$ from baseline (Visit 2) (or if serum creatinine concentration rises above 3 mg/dL (265 $\mu\text{mol/L}$)), the investigator will check for potentially reversible causes of renal dysfunction (see above).

[figure not shown]
If the investigator judges that study medication has to be stopped, he/she will have to contact the Novartis medical monitor or his/her designee. Thereafter, serum creatinine assessments will have to be repeated at least each week until levels return to acceptable values. If study medication was stopped, every effort will be done to restart it again, according to clinical conditions.

[figure not shown]

[figure not shown]

[figure not shown]

[figure not shown]

[figure not shown]

19 Appendix 7: Liver event definitions and follow-up requirements

Table 19-1 Liver event definitions

	Definition/ threshold
Adverse event of special interest	
Laboratory values	ALT or AST > 3 x ULN ALP > 2 x ULN TBL > 1.5 x ULN
Medically significant event (SAE)	
Laboratory values	ALT or AST > 5 x ULN (with or without TBL > 2 x ULN [mainly conjugated fraction]) ALP > 5 x ULN (with or without TBL > 2 x ULN [mainly conjugated fraction]) TBL > 3 x ULN Potential Hy's Law cases (defined as ALT/AST > 3 x ULN and TBL > 2 x ULN [mainly conjugated fraction] without notable increase in ALP to > 2 x ULN)
Adverse events	Any clinical event of jaundice (or equivalent term) ALT or AST > 3 x ULN accompanied by general malaise, fatigue, abdominal pain, nausea, or vomiting, or rash with eosinophilia Any event that links to a preferred term (PT) in the MedDRA dictionary falling under the SMQ sub-module "Drug-related hepatic disorders – severe events only"* or any "Hy's law case" PT

* These events cover the following: hepatic failure, fibrosis and cirrhosis, and other liver damage-related conditions; the non-infectious hepatitis; the benign, malignant and unspecified liver neoplasms

Table 19-2 Liver event follow up requirements

Criteria	Event type	Actions required	Follow-up monitoring
Potential Hy's Law case ^a	Medically significant	Discontinue the study drug immediately Hospitalize, if clinically appropriate Report to Novartis as an SAE Establish causality	ALT, AST, TBL, Alb, PT, ALP and γ GT until resolution ^c (frequency at investigator discretion)
ALT or AST			
> 8 x ULN	Medically significant	Repeat LFT within 48 hours If elevation persists, discontinue the study drug immediately Hospitalize if clinically appropriate Report to Novartis as an SAE Establish causality	ALT, AST, TBL, Alb, PT, ALP and γ GT until resolution ^c (frequency at investigator discretion)
> 5 to \leq 8 x ULN	Medically significant	Repeat LFT within 48 hours If elevation persists for more than 2 weeks , discontinue the study drug Report to Novartis as an SAE Establish causality	ALT, AST, TBL, Alb, PT, ALP and γ GT until resolution ^c (frequency at investigator discretion)
> 3 x ULN accompanied by symptoms ^b	Medically significant	Discontinue the study drug immediately Hospitalize if clinically appropriate Report to Novartis as an SAE Establish causality	ALT, AST, TBL, Alb, PT, ALP and γ GT until resolution ^c (frequency at investigator discretion)
> 3 to \leq 5 x ULN (patient is asymptomatic)	AESI	Central laboratory to report to Investigator & Novartis Repeat LFT once or twice in the week If elevation persists, establish causality	Investigator discretion Monitor LFT within 1 to 4 weeks or at next visit
\leq 3 x ULN (patient is asymptomatic)	N/A	Repeat LFT at next visit	
ALP (isolated)			
> 5 x ULN	Medically significant	Repeat LFT within 48 hours If elevation persists, report to Novartis as an SAE Establish causality	Investigator discretion Monitor LFT within 1 to 4 weeks or at next visit
> 2 to \leq 5 x ULN (patient is asymptomatic)	AESI	Central laboratory to report to Investigator & Novartis Repeat LFT once or twice in the week. If elevation persists, establish causality	Investigator discretion Monitor LFT within 1 to 4 weeks or at next visit
\leq 2 x ULN	N/A	Repeat LFT at next visit	

Criteria	Event type	Actions required	Follow-up monitoring
(patient is asymptomatic)			
TBL (isolated)			
> 3 x ULN	Medically significant	Repeat LFT within 48 hours If elevation persists, discontinue the study drug immediately Hospitalize if clinically appropriate Report to Novartis as an SAE Establish causality	ALT, AST, TBL, Alb, PT, ALP and γ GT until resolution ^c (frequency at investigator discretion) Test for hemolysis (e.g., reticulocytes, haptoglobin, unconjugated [indirect] bilirubin)
> 1.5 to \leq 3 x ULN (patient is asymptomatic)	AESI	Central laboratory to report to Novartis Repeat LFT once or twice in the week If elevation persists, establish causality	investigator discretion Monitor LFT within 1 to 4 weeks or at next visit
\leq 1.5 x ULN (patient is asymptomatic)	N/A	Repeat LFT at next visit	
Preferred terms			
Jaundice	Medically significant	Discontinue the study drug immediately Hospitalize the patient Report to Novartis as an SAE Establish causality	ALT, AST, TBL, Alb, PT, ALP and γ GT until resolution ^c (frequency at investigator discretion)
“Drug-related hepatic disorders - severe events only” SMQ AE	Medically significant	Discontinue the study drug hospitalization if clinically appropriate Report to Novartis as an SAE Establish causality	Investigator discretion

^a Elevated ALT/AST > 3 x ULN and TBL > 2 x ULN but with no notable increase in ALP to > 2 x ULN

^b General malaise, fatigue, abdominal pain, nausea, or vomiting, rash with eosinophilia

^c Resolution is defined as an outcome of one of the following: return to baseline values, stable values at three subsequent monitoring visits at least 2 weeks apart, remain at elevated level after a maximum of 6 months, liver transplantation, and death.

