7.1 Adverse events

An adverse event (AE) is any untoward medical occurrence (i.e., any unfavorable and unintended sign [including abnormal laboratory findings], symptom or disease) in a subject or clinical investigation subject after providing written informed consent for participation in the study. Therefore, an AE may or may not be temporally or causally associated with the use of a medicinal (investigational) product.

The occurrence of adverse events should be sought by non-directive questioning of the patient at each visit during the study. Adverse events also may be detected when they are volunteered by the patient during or between visits or through physical examination, laboratory test, or other assessments.

Abnormal laboratory values or test results constitute adverse events only if they fulfill at least one of the following criteria:

- they induce clinical signs or symptoms,
- they are considered clinically significant,
- they require therapy.

Clinically significant abnormal laboratory values or test results should be identified through a review of values outside of normal ranges/clinically notable ranges, significant changes from baseline or the previous visit, or values which are considered to be non-typical in patient with underlying disease. Investigators have the responsibility for managing the safety of individual patient and identifying adverse events. Alert ranges for labs and other test abnormalities are included in Appendix 1.

Adverse events should be recorded in the Adverse Events CRF under the signs, symptoms or diagnosis associated with them accompanied by the following information.

- the severity grade
 - mild: usually transient in nature and generally not interfering with normal activities
 - moderate: sufficiently discomforting to interfere with normal activities
 - severe: prevents normal activities
- its relationship to the study treatment (no/yes),
- its duration (start and end dates) or if the event is ongoing an outcome of not recovered/not resolved should be reported.
- whether it constitutes a serious adverse event (SAE)
- action taken regarding study treatment
- whether other medication or therapies have been taken (concomitant medication/non-drug therapy)
- its outcome (not recovered/not resolved; recovered/resolved; recovering/resolving, recovered/resolved with sequelae; fatal; or unknown)

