An SAE is any adverse event (appearance of (or worsening of any pre-existing) undesirable sign(s), symptom(s) or medical conditions(s) which meets any one of the following criteria

- is fatal or life-threatening
- results in persistent or significant disability/incapacity
- constitutes a congenital anomaly/birth defect
- requires inpatient hospitalization or prolongation of existing hospitalization, unless hospitalization is for :
 - routine treatment or monitoring of the studied indication, not associated with any deterioration in condition
 - elective or pre-planned treatment for a pre-existing condition that is unrelated to the indication under study and has not worsened since signing the informed consent
 - treatment on an emergency outpatient basis for an event not fulfilling any of the definitions of a SAE given above and not resulting in hospital admission
 - social reasons and respite care in the absence of any deterioration in the patient's general condition
- is medically significant, i.e. defined as an event that jeopardizes the patient or may require medical or surgical intervention to prevent one of the outcomes listed above.

All malignant neoplasms will be assessed as serious under "medically significant" if other seriousness criteria are not met.

Unlike routine safety assessments, SAEs are monitored continuously and have special reporting requirements; see [Section 7.2](#).

All adverse events should be treated appropriately. Treatment may include one or more of the following: no action taken (i.e. further observation only); investigational treatment dosage adjusted/temporarily interrupted; study drug(s) permanently discontinued; concomitant

medication given; non-drug therapy given. The action taken to treat the adverse event should be recorded on the Adverse Event CRF.

Once an adverse event is detected, it should be followed until its resolution or until it is judged to be permanent, and assessment should be made at each visit (or more frequently, if necessary) of any changes in severity, the suspected relationship to the study treatment, the interventions required to treat it, and the outcome.

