7.2 Serious adverse event reporting

To ensure patient safety, every SAE, regardless of causality, occurring after the patient has provided informed consent and until 30 days after the last study visit must be reported to Novartis within 24 hours of learning of its occurrence. Any SAEs experienced after the 30 days period should only be reported to Novartis if the investigator suspects a causal relationship to study treatment.

Recurrent episodes, complications, or progression of the initial SAE must be reported as follow-up to the original episode, regardless of when the event occurs. This report must be submitted within 24 hours of the investigator receiving the follow-up information. An SAE that is considered completely unrelated to a previously reported one should be reported separately as a new event.

Follow-up information provided should describe whether the event has resolved or continues, if and how it was treated, whether the treatment code was broken or not and whether the patient continued or withdrew from study participation. Each re-occurrence, complication, or progression of the original event should be reported as a follow-up to that event regardless of when it occurs.

If the SAE is not previously documented in the Investigator's Brochure or Package Insert (new occurrence) and is thought to be related to the investigational treatment a Drug Safety and Epidemiology Department associate may urgently require further information from the investigator for Health Authority reporting. Novartis may need to issue an Investigator Notification (IN) to inform all investigators involved in any study with the same investigational treatment that this SAE has been reported. Suspected Unexpected Serious Adverse Reactions (SUSARs) will be collected and reported to the competent authorities and relevant ethics committees in accordance with Directive 2001/20/EC or as per national regulatory requirements in participating countries.

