7.3 Liver safety monitoring

To ensure patient safety and enhance reliability in determining the hepatotoxic potential of an investigational drug, a standardized process for identification, monitoring and evaluation of liver events has to be followed.

Hepatotoxicity-related events are subject to additional safety assessments and thus are followed with a standardized questionnaire. A list of terms that are considered “hepatotoxicity-related” (e.g., cholaemia, ascites, liver disorder) will be provided to sites in a manual.

If such an event occurs that meets criteria for serious adverse event, the investigator will complete a separate questionnaire for a Hepatotoxicity and Statin-related Event form (provided by Novartis) to summarize the event, its further diagnostic tests performed, and its related information.

Liver events are divided into two categories:

- Liver events of special interest (AESI) which consist of liver function tests (LFTs) elevations
- Medically significant liver events which are considered as serious adverse events (SAEs) and which consist of marked elevations of LFTs and / or pre-specified adverse events.

Please refer to Table 19-1 in Appendix 7 for complete definitions of liver events.

Any liver event which meets the criteria for “**medically significant**” event as outlined in Table 19-1 of Appendix 7 should follow the **standard procedures for SAE reporting** as described in [Section 7.2](#).

Every liver event as defined in Table 19-1 of Appendix 7 should be followed up by the investigator or designated personal at the trial site as summarized below. Detailed information is outlined in Table 19-2 in Appendix 7.

- Repeating the LFT to confirm elevation as appropriate
- Discontinuation of the investigational drug if appropriate
- Hospitalization of the patient if appropriate
- A causality assessment of the liver event via exclusion of alternative causes (e.g., disease, co-medications)
- An investigation of the liver event which needs to be followed until resolution.

These investigations can include serology tests, imaging and pathology assessments, hepatologist’s consultancy, based on investigator’s discretion. All follow-up information, and the procedures performed should be recorded on appropriate CRF pages, including the liver event overview CRF pages.

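### For isolated ALP above 5 x ULN, Table 19-2 makes the SAE report wait for a confirmatory repeat, while Table 19-1 and Section 7.3 make the same value an SAE reportable within 24 hours

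*Protocol*

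**What the plan says.** Four places in the protocol bear on a single laboratory value, ALP above 5 x ULN.

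- **Appendix 7, Table 19-1** places "ALP > 5 x ULN (with or without TBL > 2 x ULN [mainly conjugated fraction"]) in the block headed as medically significant events, that is, SAEs. Isolated ALP is therefore included, and no repeat or confirmation is required.
- **Section 7.3** says that a liver event in this category is an SAE. Any medically significant "event as outlined in Table 19-1 of Appendix 7 should follow the" standard SAE procedure of Section 7.2.
- **Section 7.2** says that every SAE, whatever its cause, "must be reported to Novartis within 24 hours of learning of its occurrence".
- **Appendix 7, Table 19-2**, isolated ALP above 5 x ULN, also labels the value medically significant. Its actions are to repeat the liver function test within 48 hours and then: "If elevation persists, report to Novartis as an SAE".

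Section 7.3 brings in Table 19-2 under a separate sentence on follow-up: "Every liver event as defined in Table 19-1 of Appendix 7 should be followed up by the investigator". The list beneath that sentence includes "Repeating the LFT to confirm elevation as appropriate". SAP Appendix 2 reproduces the Table 19-2 row with the same condition.

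**The concern.** A site with a first ALP result above 5 x ULN finds one instruction to report within 24 hours and another to report only after a repeat test that may be taken up to 48 hours later. If the repeat has fallen, the second instruction requires no SAE report. A site acting in good faith on Table 19-2 can therefore breach Section 7.2.

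What is at stake is the timeliness and consistency of safety reporting. About 40 sites are planned. Whether an unconfirmed ALP rise reaches the SAE summaries of SAP Section 2.8.1 could depend on which text a site followed. Laboratory-based counts do not depend on SAE reporting, and the efficacy analyses are not involved.

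**Working it through.** **1. Does the text make SAE status depend on confirmation?** Table 19-1 does not. Section 7.3 ties reporting to the Table 19-1 criteria alone. Its remark on repeating the test comes later, in the follow-up list, and is qualified as a matter of appropriateness. Only the Table 19-2 row sets the condition, so the two instructions do conflict.

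**2. Is the row out of line with the rest of Table 19-2?** The table has eight medically significant rows:

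| Row | What the persistence wording is attached to |
|---|---|
| Potential Hy's Law case | none |
| ALT/AST > 8 x ULN | stopping study drug |
| ALT/AST > 5 to 8 x ULN | stopping study drug (after more than 2 weeks) |
| ALT/AST > 3 x ULN with symptoms | none |
| Isolated ALP > 5 x ULN | **the SAE report** |
| Isolated TBL > 3 x ULN | stopping study drug |
| Jaundice | none |
| Severe drug-related hepatic SMQ event | none |

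The count is 4 with no such wording, 3 tied to stopping drug and 1 tied to the report (4 + 3 + 1 = 8). In the three drug-stopping rows the SAE report reads as a separate entry. That reading relies on the layout of the extracted table. The ALP row does not rely on layout, because condition and report are one sentence.

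**3. How late can a report be?** Set hour 0 as the time the site learns of the first value, and assume the 48 hours for the repeat run from then. Let *t* be the hour of the repeat draw (0 to 48) and *r* the laboratory turnaround in hours. The deadline under Sections 7.2 and 7.3 is hour 24.

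- Reported at the moment of the repeat result: hours late = max(0, *t* + *r* − 24).
- A new 24-hour clock started at the repeat result and fully used: hours late = (*t* + *r* + 24) − 24 = *t* + *r*.

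Turnaround for repeat tests is not stated. The lower bound is *r* = 0. As an illustrative upper value I take *r* = 72, the time that Section 3.1 allows for screening results. Applying it to repeats is an assumption, although Section 3.1 does send unscheduled tests to the central laboratory.

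| *t* | *r* | Late, reported at once | Late, new clock |
|---|---|---|---|
| 0 | 0 | 0 | 0 |
| 24 | 0 | 0 | 24 |
| 48 | 0 | 48 − 24 = 24 | 48 |
| 0 | 72 | 72 − 24 = 48 | 72 |
| 48 | 72 | 120 − 24 = 96 | 120 |

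With an immediate result, a repeat drawn by hour 24 can still meet the deadline if the report goes at once. If the repeat does not confirm the elevation, the row asks for no report, so lateness does not apply.

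**4. How often could it arise?** The documents give no event rate. Under Section 6.5.4 and Table 6-2, ALP belongs to the full panel only, at Visits 1, 2 and 7. The one scheduled ALP after randomization is therefore at end of study, or at the corresponding early-withdrawal visit. Any other value would come from an unscheduled test.

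**The case against.** The best defence reads the row as a deliberate graded rule. Table 19-1 is general, and the Table 19-2 row is specific to isolated ALP. It is milder throughout, with no drug discontinuation, no hospitalization and follow-up left to the investigator, so confirming first would fit. On that reading the reportable event is the confirmed elevation, and the 24-hour clock starts only at confirmation. The mildness of the row is real. But the protocol nowhere states the exception, the row keeps the medically significant label, and Section 7.3 uses Table 19-2 for follow-up only. If the exception was intended, Table 19-1 and Section 7.3 would need to say so.

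A second argument is that a site can satisfy both texts by reporting at once, because nothing forbids an early report. That is true, but the row gives a protocol-based reason not to do so.

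A third is that exposure is small and other safeguards exist. This largely stands:

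- Exclusion criterion 21 removes cholestasis and biliary cirrhosis at entry.
- Jaundice, raised bilirubin, marked or symptomatic ALT/AST rises and Hy's Law cases each have their own SAE entry.
- The sponsor receives all central laboratory results (Section 6.5.4), and Section 6 requires safety contact for 30 days after the last visit.
- Under Section 7.1 an investigator may still treat laboratory values as adverse events because "they are considered clinically significant", or as serious where the event "is medically significant, i.e. defined as an event that jeopardizes the patient or may require medical or surgical intervention".

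These points reduce the weight of the problem. None of them starts the 24-hour clock for an isolated, silent ALP rise, for which Table 19-1 is the mandatory trigger.

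**Conclusion.** The concern holds. For isolated ALP above 5 x ULN, Table 19-2 contradicts Table 19-1 and Sections 7.2 and 7.3, and a site following it can report late or not at all. With an immediate repeat result the delay beyond the deadline runs from none to 24 hours if the report is sent at once, and up to 48 hours if a new clock is started; laboratory turnaround would add to either. These figures assume that the clock starts at the first value, as Table 19-1 and Section 7.3 imply, and that the 48 hours run from the same moment.

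The consequence is limited to reporting of an event that should be rare. It should be corrected because the safety rule is wrong as written, but it does not threaten the trial's conclusions.

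**What to change.** In the isolated-ALP above 5 x ULN row of protocol Table 19-2, remove the persistence condition so that the SAE report stands as its own action, as it reads in the other medically significant rows. Keep the repeat test within 48 hours as follow-up. Make the same edit in SAP Appendix 2 for consistency only, since the SAP does not govern site reporting.

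The opposite repair, adding a confirmation step to Table 19-1 and Section 7.3, would also remove the contradiction. It would, however, narrow the SAE definition, touch two governing places instead of one outlying row, and leave unconfirmed values unreported.

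The cost is one line in the protocol, made by written amendment under Section 11.1, and one in the SAP. Visits, data collection and analyses do not change. The downside is an occasional SAE report for an elevation that the repeat does not confirm.
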